6.2 Verification of materials

Prior to accepting the registration, registration/randomization application will verify the following:

- IRB approval at the registering institution
- Patient eligibility
- Existence of a signed consent form
- Existence of a signed authorization for use and disclosure of protected health information

6.3 Documentation of IRB approval

Documentation of IRB approval must be on file in the Registration Office before an investigator may register any patients.

In addition to submitting initial IRB approval documents, ongoing IRB approval documentation must be on file (no less than annually) at the Registration Office (fax: [REDACTED]). If the necessary documentation is not submitted in advance of attempting patient registration, the registration will not be accepted, and the patient may not be enrolled in the protocol until the situation is resolved.

When the study has been permanently closed to patient enrollment, submission of annual IRB approvals to the Registration Office is no longer necessary.

6.4 Baseline symptoms

All required baseline symptoms (see Section 10.6) must be documented and graded.

6.4a Study drug

Study drug is available on site. Each site will have a supply of both investigational product and placebo that will be sent from Nightingale Remedies. After randomization at Mayo, the local site pharmacist will re-label the product per randomization instructions. Research staff, other than pharmacy, are blinded, and will dispense the cream to the patient at the site.

6.4b Patient questionnaire booklets need to be available for patients

Patient questionnaire should be ordered using the Patient Questionnaire Order Form. PDF versions of the questionnaires will be sent electronically for printing.

Patient questionnaire booklets should be provided to the patients. They may be provided to the patient during a routine visit, via mail or electronically. They will be available as follows:

- Questionnaires for Baseline (this should be completed prior to application of study medication)
- Questionnaires for week 1 & 2 (a self-addressed and stamped envelope should be provided the patient to mail this back at the end of week 2)
- Questionnaires for week 3 & 4 (a self-addressed and stamped envelope should be provided the patient to mail this back at the end of week 4)

Before the questionnaires are provided to the patient, the patient initials and appropriate dates of when they are to be completed should be written on each of the questionnaires.

6.4c Study Conduct

The clinical trial will be conducted in compliance with regulations (21 CFR 312, 50, and 56), guidelines for Good Clinical Practice (ICH Guidance E6), and in accordance with general ethical principles outlined in the Declaration of Helsinki; informed consent will be obtained from all participating patients; the protocol and any amendments will be subject to approval by the designated IRB prior to implementation, in accordance with 21 CFR 56.103(a); and subject records will be stored in a secure location and subject confidentiality will be maintained. The investigator will be thoroughly familiar with the appropriate use of the study drug as described in the protocol and Investigator's Brochure. Essential clinical documents will be maintained to demonstrate the validity of the study and the integrity of the data collected. Master files should be established at the beginning of the study, maintained for the duration of the study and retained according to the appropriate regulations.

6.4d Randomization Procedures: The factor defined in Section 5.0 (gender) will be used as the only stratification factor

6.4e Procedures for Double-Blinding the Treatment Assignment

6.4e1 After the treatment assignment has been ascertained by the registration/randomization application, the registration specialist will notify the designated unblinded data manager/nurse/pharmacist at the patient's institution. The name of this contact person is to be entered in the designated space on the eligibility checklist at the time of registration. Make sure this contact person will be available at the time of registration so he or she can be contacted by the registration specialist if necessary. This contact person may not be involved in assessing adverse events or any other outcome measure and should not be the same person listed on page one of the Eligibility Checklist Form as the person completing the form. The last page of the Eligibility Checklist Form should provide the sources of communication, either fax or e-mail, and the appropriate contact information. The registration specialist will then communicate the treatment assignment to the designated contact at the patient's institution.

6.4e2 The treatment assignment will be to *active or placebo*. The unblinded pharmacist should only give one supply of study cream at a time according to the treatment assignment from the registration specialist. Each participating institution will be responsible for monitoring drug supplies. The bottles will be labeled by the unblinded pharmacist as "*CBD or placebo cream*" so that the contents are not discernible to the person administering the treatment. At the time of cross-over, the patient will be given the alternative medication (CBD or placebo), again in a blinded manner.

6.4e3 The unblinded pharmacist will maintain records that indicate the identity of the patient and their corresponding treatment assignment.

7.0 Protocol Treatment

7.1 Treatment Plan:

Patients will be instructed to apply the CBD or placebo cream in a thin layer (approximately 4-5 pumps of product) to affected areas twice daily for 14 days.
CIPN in hands: apply 4-5 pumps to hands twice a day
CIPN in feet: apply 4-5 pumps to feet twice a day
After two weeks of using the designated treatment participants will cross over to the other treatment. The other treatment will be applied as described above, twice daily for another two weeks.

7.2 Breaking Code:

During the study, codes should only be broken in emergency situations, which are not expected in this study. In the event of an emergency, call the MCCC Registration Office at [REDACTED] to break the code on Monday through Friday, 8:00 a.m. to 4:30 p.m. Central Time. Alternatively, email the Registration Office [REDACTED]. If the code must be broken after hours, assume the patient was assigned to active treatment and treat accordingly. Place a call to the MCCC Registration Office and leave a message informing them of the need to un-blind a patient. Provide your contact information so that MCCC Registration Office personnel can return the call the next business day.

7.3

After the patient has completed the study and the questionnaires have been completed and sent in, the code can be broken, so that the patient can choose whether to continue to use CBD on their own if they felt it gave them benefit. To do this, the MCCC Registration

Office may [REDACTED] to find out which study therapy the patient was receiving.

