10.4 Expedited Reporting Requirements for IND Agents

10.41 Phase 1 and Early Phase 2 Studies: Expedited Reporting Requirements for Adverse Events that Occur on Studies under an IND within 30 Days of the Last Administration of the Investigational Agent/Intervention^{1,2}

FDA REPORTING REQUIREMENTS FOR SERIOUS ADVERSE EVENTS (21 CFR Part 312)

NOTE: Investigators **MUST** immediately report to the sponsor **ANY** Serious Adverse Events, whether or not they are considered related to the investigational agent(s)/intervention (21 CFR 312.64)
An adverse event is considered serious if it results in **ANY** of the following outcomes:

- 1) Death
- 2) A life-threatening adverse event
- 3) An adverse event that results in inpatient hospitalization or prolongation of existing hospitalization for ≥ 24 hours
- 4) A persistent or significant incapacity or substantial disruption of the ability to conduct normal life functions
- 5) A congenital anomaly/birth defect.
- 6) Important Medical Events (IME) that may not result in death, be life threatening, or require hospitalization may be considered serious when, based upon medical judgment, they may jeopardize the patient or subject and may require medical or surgical intervention to prevent one of the outcomes listed in this definition. (FDA, 21 CFR 312.32; ICH E2A and ICH E6).

ALL SERIOUS adverse events that meet the above criteria **MUST** be immediately reported to the sponsor within the timeframes detailed in the table below.

Hospitalization	Grade 1 and Grade 2 Timeframes	Grade 3-5 Timeframes
Resulting in Hospitalization ≥ 24 hrs	7 Calendar Days	24-Hour 3 Calendar Days
Not resulting in Hospitalization ≥ 24 hrs	Not required	

Expedited AE reporting timelines are defined as:

- “24-Hour; 3 Calendar Days” - The AE must initially be reported within 24 hours of learning of the AE, followed by a complete expedited report within 3 calendar days of the initial 24-hour report.
- “7 Calendar Days” - A complete expedited report on the AE must be submitted within 7 calendar days of learning of the AE.

¹Serious adverse events that occur more than 30 days after the last administration of investigational agent/intervention and have an attribution of possible, probable, or definite require reporting as follows:

Expedited 24-hour notification followed by complete report within 3 calendar days for:

- All Grade 3, 4, and Grade 5 AEs

Expedited 7 calendar day reports for:

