11.0 Treatment Evaluation/Measurement of Effect

See statistical details in Section 16.

12.0 Descriptive Factors: Not applicable.**13.0 Treatment/Follow-up Decision at Evaluation of Patient**

Physicians can use the unblinded study data, for the individual patient, to help determine subsequent therapy for individual patients.

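### A patient's code may be released before that patient's clinician-recorded adverse events, attributions and CTCAE grades are final, with no separation of roles; sections 6.4a, 6.4e1 and 15.0 also disagree on who is unblinded

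*Combined protocol and SAP*

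**What the plan says.** **Release of the code.** During the study, section 7.2 says "codes should only be broken in emergency situations". Section 7.3 sets a different rule once a patient finishes: "After the patient has completed the study and the questionnaires have been completed and sent in, the code can be broken", and it gives the reason as "so that the patient can choose whether to continue to use CBD on their own if they felt it gave them benefit". Part of the sentence on how the code is obtained is redacted. Section 13.0 adds: "Physicians can use the unblinded study data, for the individual patient, to help determine subsequent therapy for individual patients". Neither section refers to database lock, to the last patient, or to the state of the clinician-recorded data.

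**Source of the safety data.** Under the section 4.1 footnotes and section 10.62, a research nurse or clinician collects adverse events and grades CTCAE neuropathy on weekly calls. Section 10.62 says the patient booklets are not used to document adverse events. Section 10.621 has Grade 2 events submitted only if they are judged at least possibly related. Section 17.1 allows two weeks after patient submission for the week-2 and week-4 data.

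**Who is unblinded.** Section 6.4a says: "Research staff, other than pharmacy, are blinded, and will dispense the cream to the patient at the site". Section 15.0 likewise leaves only the local pharmacist unblinded. Section 6.4e1 is wider: "the registration specialist will notify the designated unblinded data manager/nurse/pharmacist". It also bars that contact from assessing adverse events or any other outcome.

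**The concern.** The condition for release protects the patient-reported data but not the data recorded by staff. Once the booklets are in the post, the code can be opened while adverse events from weeks 1 to 4 still await entry, attribution or query resolution. In a two-period crossover one opened code reveals which cream was used in both periods, so every event still to be settled could be attributed with that knowledge.

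Comparing side effects with placebo is the second aim under section 2.1. For Grade 2 events the relatedness judgement decides whether the event is submitted at all, so a judgement made with the code known could tilt the comparison. The same applies, less directly, to CTCAE neuropathy, a secondary endpoint graded by telephone. There is also a weaker route to later patients: staff who know how earlier patients fared on each cream could carry that impression into later calls.

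**Working it through.** The plan's only design figure is the power table in section 16.1. A noncentral t calculation (38 degrees of freedom, noncentrality d × √(20/2), two-sided alpha 0.05) gives 0.338, 0.456, 0.578, 0.693, 0.792 and 0.869 for effect sizes 0.5 to 1.0. These agree with the stated 0.34, 0.46, 0.58, 0.69, 0.79 and 0.87. The point here neither disputes nor changes them.

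The rest is a comparison of sections.

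1. **Trigger against data source.** Section 7.3 is satisfied by study completion and returned questionnaires. Section 10.62 takes adverse events from the calls and excludes the booklets as a source. Returned booklets therefore say nothing about whether grades, events and attributions have been entered.
2. **Length of the gap.** The last call and the last booklet both fall at the end of week 4. Section 17.1 gives two weeks from patient submission for the week-4 data. If that limit is taken to cover the call data too, which the section does not spell out, the code can be open for up to about 14 days before the clinician data are due.
3. **What attribution controls.**

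| Event | Does reporting depend on attribution? | Section |
|---|---|---|
| Grade 2, routine reporting | Yes | 10.621 |
| Grade 3 and 4 | No | 10.622 |
| Serious, within 30 days of last application | No | 10.0, 10.41 |
| Serious, later than 30 days | Yes | 10.41, footnote 1 |

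   The main exposure is therefore Grade 2 events from weeks 1 to 4 whose attribution is entered or revised after release.
4. **Sensitivity of the comparison.** Section 16.2 compares incidence between arms with Fisher's exact test. As an illustration with 20 per arm and all events in one arm, the two-sided p-value for k events against 0 is 2 × C(20,k) / C(40,k).
   - k = 5: 2 × 15,504 / 658,008 = 0.047
   - k = 4: 2 × 4,845 / 91,390 = 0.106

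   With counts this small, one reclassified event can change how the result reads, even in an exploratory analysis. This shows sensitivity; it does not predict how many events would be reclassified.
5. **Separation of roles.** Section 13.0 gives the code to physicians, and sections 4.1 and 10.62 name clinicians among those who make the calls. No section says these must be different people, or that someone who learns a code stops attributing that patient's events or assessing others.
6. **Ceiling on exposure.** Release is per patient, so at most 40 − 1 = 39 patients could have their codes opened before the last one finishes. This is an upper limit, not an estimate.
7. **Unblinded roles.** Sections 6.4a and 15.0 name pharmacy only; 6.4e1 also allows a data manager or nurse; 6.4e2 and 6.4e3 return to the unblinded pharmacist. These cannot all stand as written.

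**The case against.** The case for leaving the plan alone is substantial. Adverse events are elicited on calls made while the blind is in force, and most serious or severe events are reported whatever the attribution. The rule in 7.3 serves the patient's own decision. This is a descriptive pilot of 40 patients, and late-occurring events are handled through a Forms Packet (10.7) that is not in the documents. All of this stands and limits the point to late entry or revision, mainly of Grade 2 attributions. It does not remove the point, because nothing requires those judgements to be recorded before the code is opened.

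A reader might infer more than the text supports:

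- **That every code is opened at week 4 to site staff.** Section 7.3 is permissive, applies after completion, and names no site recipient in the visible text. Section 13.0 names physicians only. That they also make study assessments is plausible but not stated.
- **That efficacy results are compromised.** The primary endpoint is the patient's own report at week 2. It is due well before 7.3 applies, so that patient's value is not affected.
- **That the code should be held for the whole serious-event period.** Section 10.41 covers events "within 30 Days of the Last Administration of the Investigational Agent/Intervention", but serious events in that window are reported regardless of attribution, so holding the code for it gains little.
- **That opened codes let staff predict later assignments.** This needs a blocked scheme, and the randomisation method is not given. Gender is the only stratification factor, and assignment is made centrally. Later patients remain blinded.
- **That 6.4e1 puts an unblinded person in charge of assessments.** It expressly forbids that. What remains is a disagreement about roles; data entry and query handling are not mentioned in the bar, but no section gives those tasks to the contact.

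**Conclusion.** The point holds in a limited form. Sections 7.3 and 13.0 permit a patient's code to be opened during the trial on a condition that does not ensure the clinician-recorded data are final, and no separation of roles follows. The exposure is mainly to Grade 2 attributions, and to CTCAE grades if they are entered or revised after release. A lesser exposure, to the assessment of later patients, arises only if the people who learn codes also make study calls.

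The bias cannot be quantified from the documents. The gap of up to about two weeks assumes that 17.1 governs the call data. The conflict between 6.4e1 and sections 6.4a and 15.0 is real but secondary. This is an inexpensive improvement to the blinding of the side-effect comparison, not a threat to the primary analysis.

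**What to change.** - **Section 7.3:** allow non-emergency release only after that patient's week-4 CTCAE grades, adverse events and attributions have been entered and queries on them closed. Have the Registration Office or the unblinded pharmacist give the result to the patient or treating physician, not to staff who make study assessments. Where a treating physician is also a study assessor, say who takes over any remaining attribution for that patient.
- **Section 13.0:** make use of the unblinded data subject to the same condition.
- **Sections 6.4a, 6.4e1 and 15.0:** reconcile them on which roles may be unblinded. Naming the pharmacist alone in 6.4e1 would match the other two sections. If another role is needed at some sites, 6.4a and 15.0 should say so, and the bar in 6.4e1 should extend to entering outcome data and resolving queries.

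The cost is a protocol wording change and a short wait, about two weeks under 17.1, before patients learn their sequence. The Registration Office and pharmacist already hold the codes. Emergency code-breaking under 7.2 is unchanged, and decisions on later therapy stay with patient and physician.

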8.0 Dosage Modification Based on Adverse Events

There are no dosage modifications. If patients develop any intolerance or bothersome enough side-effect, they are to stop the study drug/placebo. Ideally, they will still complete the study questionnaires.

9.0 Ancillary Treatment/Supportive Care:

This protocol should not interfere with appropriate supportive care measures unrelated to a patient's CIPN, unless use of CBD is specifically restricted.

10.0 Adverse Event (AE) Monitoring and Reporting

The site principal investigator is responsible for reporting any/all serious adverse events to the sponsor as described within the protocol, regardless of attribution to study agent or treatment procedure.

The sponsor/sponsor-investigator is responsible for notifying FDA and all participating investigators in a written safety report of any of the following:

- Any suspected adverse reaction that is both serious and unexpected.
- Any findings from laboratory animal or *in vitro* testing that suggest a significant risk for human subjects, including reports of mutagenicity, teratogenicity, or carcinogenicity.
- Any findings from epidemiological studies, pooled analysis of multiple studies, or clinical studies, whether or not conducted under an IND and whether or not conducted by the sponsor, that suggest a significant risk in humans exposed to the drug
- Any clinically important increase in the rate of a serious suspected adverse reaction over the rate stated in the protocol or Investigator's Brochure (IB).

Summary of SAE Reporting for this study
(please read entire section for specific instructions):

WHO:	WHAT form:	WHERE to send:
All sites	Pregnancy Reporting	Mayo Sites – attach to MCCC Electronic SAE Reporting Form [REDACTED] Will automatically be sent to [REDACTED] [REDACTED] Non Mayo sites – complete and forward to [REDACTED]
Mayo Clinic Sites	Mayo Clinic Cancer Center SAE Reporting Form: [REDACTED]	Will automatically be sent to [REDACTED] [REDACTED]
Mayo Clinic Sites	Mayo Clinic Cancer Center SAE Reporting Form [REDACTED] AND attach MedWatch 3500A: [REDACTED]	Will automatically be sent to [REDACTED] [REDACTED]
Non-Mayo Clinic Sites	MedWatch 3500A: [REDACTED]	[REDACTED]

Definitions

Adverse Event

Any untoward medical occurrence associated with the use of a drug in humans, whether or not considered drug related.

Suspected Adverse Reaction

Any adverse event for which there is a reasonable possibility that the drug caused the adverse event.

Expedited Reporting

Events reported to sponsor within 24 hours, 5 days or 10 days of study team becoming aware of the event.

Routine Reporting

Events reported to sponsor via case report forms

Events of Interest

Events that would not typically be considered to meet the criteria for expedited reporting, but that for a specific protocol are being reported via expedited means in order to facilitate the review of safety data (may be requested by the FDA or the sponsor).

10.1 Adverse Event Characteristics

CTCAE term (AE description) and grade: The descriptions and grading scales found in the revised NCI Common Terminology Criteria for Adverse Events (CTCAE) version 5.0 will be utilized for AE reporting. All appropriate treatment areas should have access to a copy of the CTCAE version 5.0. A copy of the CTCAE version 5.0 can be downloaded from the CTEP web site:

- a. Identify the grade and severity of the event using the CTCAE version 5.0.
- b. Determine whether the event is expected or unexpected (see Section 10.2).
- c. Determine if the adverse event is related to the study intervention (agent, treatment or procedure) (see Section 10.3).
- d. Determine whether the event must be reported as an expedited report. If yes, determine the timeframe/mechanism (see Section 10.4).
- e. Determine if other reporting is required (see Section 10.5).
- f. Note: All AEs reported via expedited mechanisms must also be reported via the routine data reporting mechanisms defined by the protocol (see Sections 10.6 and 18.0).

NOTE: A severe AE is NOT the same as a serious AE, which is defined in Section 10.4.

10.2 Expected vs. Unexpected Events

Expected events - are those described within the Section 15.0 of the protocol, the study specific consent form, package insert (if applicable), and/or the investigator brochure, (if an investigator brochure is not required, otherwise described in the general investigational plan).

Unexpected adverse events or suspected adverse reactions are those not listed in Section 15.0 of the protocol, the study specific consent form, package insert (if applicable), or in the investigator brochure (or are not listed at the specificity or severity that has been observed); if an investigator brochure is not required or available, is not consistent with the risk information described in the general investigational plan.

Unexpected also refers to adverse events or suspected adverse reactions that are mentioned in the investigator brochure as occurring with a class of drugs but have not been observed with the drug under investigation.

An investigational agent/intervention might exacerbate the expected AEs associated with a commercial agent. Therefore, if an expected AE (for the commercial agent) occurs with a higher degree of severity or specificity, expedited reporting is required.

NOTE: *The consent form may contain study specific information at the discretion of the Principal Investigator; it is possible that this information may NOT be included in the protocol or the investigator brochure. Refer to protocol or IB for reporting needs.

